5.5 Study schedule

Procedure	At Enrollment	Within 1 day of delivery	Postpartum, in house	Postpartum, at home	Up to 10 days after discharge	Postpartum 6 weeks
Inclusion/exclusion and demographics	Х	Х				
Randomization	Х	X				
Start intervention/ placebo		Х				
Intervention/placebo			X	X		
Blood pressure collection	Х		X	X	Х	X
Maternal outcomes						X

5.6 Removal of Subjects from Study

Patients can be taken off the study at any time at their own request, or they may be withdrawn at the discretion of the investigator for safety, behavioral or administrative reasons. The reason(s) for discontinuation will be documented and may include:

- 5.4.1 Patient voluntarily withdraws from treatment (follow-up permitted);
- 5.4.2 Patient withdraws consent (termination of treatment and follow-up);
- 5.4.3 Patient is unable to comply with protocol requirements;
- 5.4.4 Patient experiences toxicity that makes continuation in the protocol unsafe;
- 5.4.5 Treating physician judges continuation on the study would not be in the patient's best interest;
- 5.4.6 Lost to follow-up.

If a research subject cannot be located to document outcomes after a period of 2 weeks, the subject may be considered "lost to follow-up." All attempts to contact the subject during the first 2 weeks after discharge will be documented and will not exceed more than 2 phone texting messages and 1 phone call with or without voicemails.

5.4.6 The study is stopped.

5.7 Protections Against Physical Risk

There is minimal risk to use of furosemide in the postpartum period. Furosemide is a commonly used drug in postpartum period and prior studies have not shown any adverse effects in this patient population. At the Hospital of University of Pennsylvania, furosemide has been used frequently as part of a postpartum hypertension protocol. A DSMB comprised of individuals who are not investigators on the trial will be utilized to monitor for adverse outcomes. A list of mandatory events that should be reported to the DSMB within 24 hours of occurrence will be supplied to all clinicians and research coordinators managing trial patients. The DSMB will stop the trial if there is a 20% increase in the rates of adverse outcomes (a composite outcome). The DSMB will review the data every 6 months. Also all serious adverse effect will be recorded and reported to the institutional review board.

5.8 Protection against Loss of Privacy/Breech of Confidentiality

In order to protect a potential subject's privacy, study staff will only approach potential subjects in a private setting. Once consented, we will take multiple steps to protect the study subject from breach of confidentiality. The list linking the subject's name and medical record number will be kept behind the hospital firewall in a password-protected file. This file is only accessible through the hospital server to those individuals given password approval to access the file. Furthermore, the electronic database (REDCap) will be coded with a unique study identifier rather than with any individually identifiable private information. No PHI will be shared with anyone outside the institution.

6 Response Criteria

6.1 Criteria for initiation of therapy

Therapy will be given after 6 hours from delivery.

Safety/tolerability

Analyses will be performed for all patients having received at least one dose of study drug.

7 ADVERSE EVENTS

7.1 Adverse Event Monitoring

Adverse event data collection and reporting will be done to ensure the safety of subjects who will enroll be enrolled in thus study. Adverse events will be reported in a routine manner at scheduled times during the trial. Additionally, certain adverse events will be reported in an expedited manner to allow for optimal monitoring of patient safety and care.

All patients experiencing an adverse event, regardless of its relationship to study drug/device, will be monitored until:

- the adverse event resolves or the symptoms or signs that constitute the adverse event return to baseline;
- > any abnormal laboratory values have returned to baseline;
- there is a satisfactory explanation other than the study drug for the changes observed; or
- death.

7.2 Definitions

7.2.1 Definition of Adverse Event

An adverse event (AE) is any untoward medical occurrence in a patient receiving study treatment and which does not necessarily have a causal relationship with this treatment. An AE can therefore be any unfavorable and unintended sign (including an abnormal laboratory finding), symptom, or disease temporally associated with the use of an experimental intervention, whether or not related to the intervention.

7.2.2 Severity of Adverse Events

The severity of an AE is graded as follows:

Mild (grade 1): the event causes discomfort without disruption of normal daily activities.

Moderate (grade 2): the event causes discomfort that affects normal daily activities.

Severe (grade 3): the event makes the patient unable to perform normal daily activities or significantly affects his/her clinical status.

Life-threatening (grade 4): the patient was at risk of death at the time of the event.

Fatal (grade 5): the event caused death.

7.2.3 Serious Adverse Events

A "serious" adverse event is defined in regulatory terminology as any untoward medical occurrence that:

- **7.2.3.1** Results in death.
 - If death results from (progression of) the disease, the disease should be reported as event (SAE) itself.
- **7.2.3.2** Is life-threatening (i.e. the patient was at risk of death at the time of the event).
- **7.2.3.3** Requires in-patient hospitalization or prolongation of existing hospitalization for \geq 24 hours.
- **7.2.3.4** Results in persistent or significant disability or incapacity.
- 7.2.3.5 Is an important medical event. Essentially, any event that does not meet the above criteria, but that in the judgment of the investigator jeopardizes the patient, may be considered for reporting as a serious adverse event.

For the purposes of this study, the adverse events that would meet any of these criteria are: maternal death, ICU admission, stroke, seizure, myocardial infarction, and cardiomyopathy will be documented and reported as a SAE. In addition, any unexpected event which the PI believes to have been cause or contributed to by the intervention, regardless of whether it resulted in hospitalization, will also be considered an AE or SAE (e.g., severe allergy or anaphylaxis due to furosemide).

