Guidelines from national organizations such as the American College of Obstetrics and Gynecology (ACOG) recognize the growing concern with postpartum hypertension and have put forth specific guidelines on how to monitor for hypertension postpartum. This includes educating patients of signs and symptoms of pre-eclampsia, monitoring blood pressures for 72 hours in the hospital prior to discharge, and checking an ambulatory blood pressure within 10 days of delivery. However, only checking blood pressures 7 to 10 days after delivery is likely missing a significant number of patients. Several studies note that only 28 to 57% of patients PPHTN have their blood pressure normalize within 3 days^{12,13} Furthermore, data out of our own institution noted that 6% of women with HDP were readmitted within 3 to 14 days for hypertension related reasons. Therefore, interventions to improve the care of women with PPHTN are urgently needed.

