2.3.2 Secondary endpoints

- 2.3.2.1 Number of readmission/ ER visit that is hypertension related
- **2.3.2.2** Frequency of severe hypertension (SBP>160mmHg or DBP>110mmHg)
- **2.3.2.3** Number of days required until blood pressure resolution (<140/90 for 2 days)
- 2.3.2.4 Postpartum length of stay
- 2.3.2.5 Complications during hospitalization related to hypertensive disorders of pregnancy (acute pulmonary edema, acute kidney injury, disseminated intravascular coagulation, stroke or myocardial infarction, eclampsia, ICU stay, maternal death)
- **2.3.2.6** Adverse effects secondary to furosemide

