7.4.2 Routine Reporting

All other adverse events- such as those that are expected, or are unlikely or definitely not related to the study participation- are to be reported annually as part of regular data submission.

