8 DRUG/DEVICE INFORMATION

8.1 Furosemide

- Other names for the drug: Lasix
- Classification type of agent: Loop diuretic; Antihypertensive
- Mode of action: inhibits reabsorption of sodium and chloride in the ascending loop of Henle and distal renal tubule, interfering with the chloride-binding co-transport system, thus causing increased excretion of water, sodium, chloride, magnesium, and calcium
- Protocol dose: 20 mg, daily
- Route of administration for this study: Oral
- Incompatibilities: NSAIDs may diminish the diuretic effect of loop diuretics. Loop diuretics may enhance the nephrotoxic effect of NSAIDs. Monitoring for evidence of kidney injury or decreased therapeutic effects of loop diuretics with concurrent use of an NSAID.
- Availability: commercially available, on formulary
- Side effects: ototoxicity, mood changes, confusion, muscle pain, palpitations, dizziness, syncope, increased thirst, fatigue, weakness, decreased appetite, dry mouth, dry eyes, upset stomach, nausea, and emesis associated with fluid and electrolyte problems (Please refer to the manufacturer's package insert for a complete list of adverse events)
- Nursing implications: PO administration should be on empty stomach

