9 STUDY DESIGN/STUDY ENDPOINTS

This will be a prospective, randomized, double-blinded, single center study of the impact of a short course of furosemide on postpartum blood pressure recovery in women with hypertensive disorders of pregnancy (HDP). Please refer to Section 2.4 for end points.

Regarding stopping rules for safety or efficacy, we do not anticipate early termination of the study for either. Issues that would be of concern would be persistent hypokalemia (< 3.0) with therapy, ineffectiveness of therapy (as defined by the use of the same dosing of other antihypertensive agents for blood pressure control), and unexpected events (admission to ICU). Other findings that could trigger a safety review include the number of SAEs overall, the number of occurrences of a particular type of SAE, severe AEs, or increased frequency of events.

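### Section 7.2.3 defines a serious adverse event in two ways that conflict: a hospitalization of 24 hours or more meets the criteria but is missing from a study list worded as complete

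*Combined protocol and SAP*

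**What the plan says.** Section 7.2.3 opens with general criteria for seriousness. Item 7.2.3.3 covers an event that "Requires in-patient hospitalization or prolongation of existing hospitalization" for 24 hours or more. Other items cover death, threat to life, lasting disability, and important medical events at the investigator's discretion.

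The closing paragraph then turns to this study and states that "the adverse events that would meet any of these criteria are: maternal death, ICU admission, stroke, seizure, myocardial infarction, and cardiomyopathy". The sentence goes on to say that these will be documented and reported as SAEs, so its grammar breaks partway. One addition follows: an unexpected event that the investigator believes the intervention caused or contributed to counts as an AE or SAE, hospitalized or not.

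Four other places depend on this definition or overlap with it:

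- Section 7.4.1 requires the investigator to be told of any SAE within 24 hours, whatever its attribution, up to 30 days after the last dose. Under 7.4.2 all other adverse events "are to be reported annually as part of regular data submission".
- Section 9 says that findings which could trigger a safety review include "the number of SAEs overall, the number of occurrences of a particular type of SAE". It then adds severe AEs and a rise in event frequency.
- Endpoint 2.3.2.5 lists "acute pulmonary edema, acute kidney injury, disseminated intravascular coagulation" beside stroke or myocardial infarction, eclampsia, ICU stay and maternal death. Endpoint 2.3.2.1 counts hypertension-related readmissions and ER visits.
- Section 1.1 reports that, at this institution, "6% of women with HDP were readmitted within 3 to 14 days for hypertension related reasons".

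**The concern.** The two halves of 7.2.3 give different answers for the same patient. Take a woman readmitted for two days with hypertension and no listed event. She meets 7.2.3.3, but she is not among the events that the next paragraph says meet any of the criteria. Staff filling in the SAE form have no rule for choosing between the two.

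The choice matters because SAE status decides the reporting route (24 hours or annual) and whether the event enters the SAE counts named in section 9. Readmission is the commonest such event that the documents allow one to foresee. Kidney injury and pulmonary edema are also of natural interest in a diuretic trial, and the protocol already collects both as complications.

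**Working it through.** The plan states no SAE count and no numeric threshold, so there is no figure to reproduce. The check compares texts first and then sizes the gap.

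**1. Criteria against list.** The six named events contain one hospitalization item, ICU admission. A ward readmission of 24 hours or more satisfies 7.2.3.3 by definition and is not listed. The linking verb is *are*, not *include*, which reads as a complete list; the broken grammar leaves room to read it as examples. The text does not settle which is meant.

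**2. List against endpoint 2.3.2.5.** Stroke, myocardial infarction, eclampsia (as seizure), ICU stay and maternal death all have a counterpart on the SAE list. Acute kidney injury, pulmonary edema and DIC do not. Omitting them is not a contradiction in itself, because a diagnosis is serious only when the case meets a criterion. The conflict arises for a case that does, for example one that is life-threatening or prolongs the stay by at least 24 hours. Pulmonary edema and raised creatinine can also be qualifying features at entry (3.1.1), so only new occurrences are at issue.

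**3. Does the added sentence close the gap?** It requires the event to be both unexpected and attributed to the intervention by the investigator. A readmission put down to the underlying disease fails the second test, as does a complication that the blinded investigator does not attribute to treatment. Section 7.4.1, by contrast, applies to SAEs whatever their attribution.

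**4. Size of the gap for readmissions.** Inputs:

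- N = 385 randomized (section 9.1). As a check, N = 350, which is 2 × 175, reading the 175 in 9.1 as per arm (350 × 1.1 = 385).
- r = 0.06, hypertension readmission within 3 to 14 days (section 1.1). This window lies inside the SAE reporting period.
- s = share of readmissions lasting at least 24 hours. The documents do not give it; it is assumed and varied from 25% to 100%.

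Expected SAEs under 7.2.3.3 = N × r × s, both arms together:

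- s = 100%: 385 × 0.06 = 23.1 (binomial 95% range 14 to 33); 350 × 0.06 = 21.0 (13 to 30)
- s = 75%: 23.1 × 0.75 = 17.3
- s = 50%: 23.1 × 0.50 = 11.6
- s = 25%: 23.1 × 0.25 = 5.8

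Under the list read as exhaustive, a readmission without a listed event adds 0, barring the unexpected and attributed case in step 3. The readings therefore differ by about 6 to 23 SAEs. Any readmission that includes a listed event counts both ways and narrows the difference. No rates are given for kidney injury, pulmonary edema or DIC, so that part cannot be sized.

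**5. Timing.** A 20-month study has one annual reporting point before it ends (20/12 = 1.7) and room for three 6-monthly DSMB reviews (20/6 = 3.3).

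**The case against.** The strongest reply is that safety review does not hang on the SAE label. Section 9 also names severe AEs and increased frequency of events, so a severe kidney injury can prompt review without being called an SAE, and ICU admission catches the gravest cases. Section 5.7 gives the DSMB 6-monthly data review, a stopping rule on a composite that is not stated as an SAE count, and a separate list of events to be reported to it within 24 hours. That list and the DSMB document mentioned in 10.4.1 are not in the file, so whether they cover these events cannot be judged. Readmissions and in-hospital complications are collected as endpoints in any case. All of this stands and limits the consequence.

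Four stronger readings that a reader might infer are not supported:

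- **That renal and fluid events never reach safety review or the SAE count.** The routes above remain open. Under 7.3, expected means previously identified as resulting from the drug, and these diagnoses are not among the side effects in 8.1. The package insert, which 7.3 also names, is not in the file. A case judged unexpected and treatment-related could still be counted.
- **That 8.1 names kidney injury as a side effect of furosemide itself.** The line "Loop diuretics may enhance the nephrotoxic effect of NSAIDs" stands under incompatibilities and concerns use together with NSAIDs.
- **That reported SAE rates would be uninterpretable, or swamped by readmissions.** The documents give no rates for other SAEs, and comparisons by arm survive through the endpoints.
- **That sites would diverge.** This is a single-center trial; the inconsistency would be between staff or over time.

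None of this removes the conflict. The backstops do not say which half of 7.2.3 governs, and 7.2.3 does not refer to them. Endpoint 2.3.2.5 is worded for complications during hospitalization, so it may not reach events after discharge.

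**Conclusion.** The inconsistency is real and sits within one section. It is a conflict between two stated rules, not a missing detail. The firmest part is readmission of 24 hours or more, which meets 7.2.3.3 and is absent from a list worded as complete. Acute kidney injury, pulmonary edema and DIC belong to the point only when newly occurring and meeting a general criterion.

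If the list is followed as exhaustive, the cases it leaves out lose the 24-hour notice to the investigator, pass to annual reporting, and drop out of the SAE counts in section 9. That section says only that such counts could trigger a review and sets no threshold, so no effect on the DSMB stopping rule is shown.

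The size, about 6 to 23 SAEs among 385 women, rests on the institution's 6% rate applying to trial participants, on the assumed 25% to 100% share lasting at least 24 hours, and on few of these readmissions including a listed event.

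**What to change.** State in 7.2.3 that the general criteria govern and that the six named events are examples. Add as further examples any readmission of 24 hours or more, and acute kidney injury, pulmonary edema or DIC when newly occurring and meeting a criterion.

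Report these under 7.4.1 as it stands, and tabulate them by arm at each 6-monthly DSMB review. If hypertension-only readmissions are meant to be exempt from individual 24-hour notice, 7.4.1 must be amended to say so, because it now applies to every SAE whatever the attribution. Exempting them in 7.2.3 alone would create a new conflict.

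The cost is one paragraph, an update to the SAE form, and a sentence in 7.4.1 if an exemption is wanted. The downside is about 6 to 23 more readmission SAE records, for events already collected as endpoint 2.3.2.1, plus any qualifying complications.

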7.3 Steps to Determine If an Adverse Event Requires Expedited Reporting

Step 1: Identify the type of adverse event

Step 2: Grade the adverse event

Step 3: Determine whether the adverse event is related to the protocol therapy Attribution categories are as follows:

- Definite The AE is clearly related to the study treatment.
- Probable The AE is likely related to the study treatment.
- Possible The AE *may be related* to the study treatment.
- Unrelated The AE is clearly NOT related to the study treatment.

Step 4: Determine the prior experience of the adverse event.

Expected events are those that have been previously identified as resulting from administration of the agent. An adverse event is considered unexpected, for expedited reporting purposes only, when either the type of event or the severity of the event is not listed in:

- the current known adverse events listed in the Agent Information Section of this protocol;
- the drug package insert;
- · the current Investigator's Brochure

7.4 Reporting Requirements for Adverse Events

7.4.1 Expedited Reporting

- The Principal Investigator will be notified within 24 hours of learning of any serious adverse events, regardless of attribution, occurring during the study or within 30 days of the last administration of the study drug.
- The University of Pennsylvania IRB must be notified within 10 business days of "any unanticipated problems involving risk to subjects or others" (UPR/UPIRSO).

The following events meet the definition of UPR:

- Any serious event (injuries, side effects, deaths or other problems), which in the opinion of the Principal Investigator was unanticipated, involved risk to subjects or others, and was possibly related to the research procedures.
- Any serious accidental or unintentional change to the IRB-approved protocol that alters the level of risk.
- 3. Any deviation from the protocol taken without prior IRB review to eliminate apparent immediate hazard to a research subject.
- 4. Any new information (e.g., publication, safety monitoring report, updated sponsor safety report), interim result or other finding that indicates an unexpected change to the risk/benefit ratio for the research.
- 5. Any breach in confidentiality that may involve risk to the subject or others.
- 6. Any complaint of a subject that indicates an unanticipated risk or that cannot be resolved by the Principal Investigator.

7.4.2 Routine Reporting

All other adverse events- such as those that are expected, or are unlikely or definitely not related to the study participation- are to be reported annually as part of regular data submission.

7.5 Stopping Rules

This study does not have a primary safety endpoint or place study subjects at high risk. Please refer to section 11.2 for further discussion of Data Safety Monitoring.

8 DRUG/DEVICE INFORMATION

8.1 Furosemide

- Other names for the drug: Lasix
- Classification type of agent: Loop diuretic; Antihypertensive
- Mode of action: inhibits reabsorption of sodium and chloride in the ascending loop of Henle and distal renal tubule, interfering with the chloride-binding co-transport system, thus causing increased excretion of water, sodium, chloride, magnesium, and calcium
- Protocol dose: 20 mg, daily
- Route of administration for this study: Oral
- Incompatibilities: NSAIDs may diminish the diuretic effect of loop diuretics. Loop diuretics may enhance the nephrotoxic effect of NSAIDs. Monitoring for evidence of kidney injury or decreased therapeutic effects of loop diuretics with concurrent use of an NSAID.
- Availability: commercially available, on formulary
- Side effects: ototoxicity, mood changes, confusion, muscle pain, palpitations, dizziness, syncope, increased thirst, fatigue, weakness, decreased appetite, dry mouth, dry eyes, upset stomach, nausea, and emesis associated with fluid and electrolyte problems (Please refer to the manufacturer's package insert for a complete list of adverse events)
- Nursing implications: PO administration should be on empty stomach

8.1.1 Product Preparation/Packaging, Receipt and Storage

Investigational Drug Service (IDS) of the University of Pennsylvania will purchase commercial furosemide 20mg tablets. These will be over-encapsulated into gelatin capsule shells and backfilled with Lactose Monohydrate, NF. The finished furosemide capsules will be placed in a light protected Type 2 HDPE plastic container with a tightly sealing lid. An internal lot number and use-by date will be assigned. The use-by date will be 12 month or the remaining expiration of any component (whichever is less). Visually-matching placebo capsules will be prepared by backfilling Lactose Monohydrate, NF into gelatin capsule shells. The finished placebo capsules will be placed in a light protected Type 2 HDPE plastic container with a tightly sealing lid. An internal lot number and use-by date will be assigned. The use-by date will be 12 month or the remaining expiration of any component (whichever is less).

IDS will dispense patient-specific study medication. IDS will package and deliver the drugs or study coordinators will pick them up as needed for participants. Drug accountability will be maintained by IDS and study coordinators.

Study medication (furosemide) will be stored at room temperature at IDS research pharmacy. Temperature is monitored in the investigational pharmacy daily. Once the

study medication or placebo are up on the floor, they will be stored at room temperature at a secure area for medications only accessible by floor and research staff.

